4.6. Composition of the test product

The test product TripleA consists of an alcohol meter, a mobile phone with an installed app, a micro-USB charger, instructions for use and extra blow nozzles. The blowing nozzle that will be placed in the user's mouth is made of a biocompatible plastic material (Cyclooy HC1204HF-8H5D003).

Ethyl glucuronide (EtG) and ethyl sulfate (EtS) are conjugated ethanol metabolites that are commonly measured in urine samples but can also be measured in blood and hair samples. EtG and EtS in urine are used as markers to detect alcohol consumption or confirm sobriety during the last 24 hours. A minor to moderate alcohol intake can be detected for up to 1 day and intoxication for up to a couple of days afterwards. EtG and EtS are eliminated more slowly than ethanol and therefore they can be used even after the ethanol has disappeared from the body. (Helander 2011).

Phosphatidylethanol (PEth) is a group of membrane lipids formed from phosphatidylcholine in the presence of ethanol and measured in whole blood. PEth is used as a marker to demonstrate regular alcohol consumption and "risk use" or to confirm sobriety in recent weeks (Helander 2011). PEth is specific for alcohol, but does not detect occasional intoxication. The half-life is 4-7 days (Helander 2011, Helander et al 2012). The concentration of PEth-16: 0/18: 1 in the blood reflects the alcohol consumption of recent weeks. PEth-16: 0/18: 1 values lower than 0.05 µmol / L indicate no or low sporadic alcohol consumption. Values between 0.05-0.30 µmol / L speak for regular moderate consumption, but even occasional very large intakes of alcohol can probably give measured values in this range. (Sampling instructions B-Phosphatidylethanol, Karolinska University Laboratory).

Low carbohydrate transferrin (CDT) shows alcohol-induced change in the glycosylation pattern of transferrin, which is measured in serum samples. CDT is used as a marker to demonstrate regular alcohol consumption and «risk use / abuse», where the measured value reflects the intake during the last weeks - the month. Single major alcohol intakes do not affect CDT levels. The specificity is controversial, as an elevated CDT value may have causes other than alcohol.

Within the framework of the current study, PEth and CDT will be analyzed.

4.7. Evaluation of the results of the relevant preclinical tests/assessments performed to justify the use of the test product in human subjects

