7.3.7. Biological samples (blood and urine)

Samples are ordered via the medical record system, taken and handled according to regular clinical routine. Patients are instructed to leave the samples some week before the visits, so that test results are available for the visit.

For sampling instructions, refer to the latest updated versions on the Academic Laboratory's website.

Urine samples for drug screening usually include amphetamine, benzodiazepines, burprenorphine, cannabis, cocaine, methadone metabolites, opiates. Verification analysis in the event of a positive result on a urine dipstick is performed if clinically relevant

Time: Done at visit 1

Phosphatidylethanol (PEth) is analyzed at Karolinska Laboratory. The concentration of PEth-16:0/18:1 is given in the unit $\mu\text{mol} / \text{L}$. The PEth level in the blood reflects the alcohol consumption of recent weeks. PEth-16:0/18:1 values lower than $0.05 \mu\text{mol} / \text{L}$ indicate no or low sporadic alcohol consumption. Values between $0.05-0.30 \mu\text{mol} / \text{L}$ speak for regular moderate consumption, but even occasional very large intakes of alcohol can probably give measured values in this range.

Time: Made at each visit

Low carbohydrate transferrin (CDT) shows alcohol-induced change in the glycosylation pattern of transferrin, which is measured in serum samples. CDT is used as a marker to demonstrate regular alcohol consumption and «risk use / abuse», where the measured value reflects the intake during the last weeks - the month. Single major alcohol intakes do not affect CDT levels.

Analyzed at the Academic Laboratory and reported in%. Reference interval $<2.0\%$.

Time: Made at each visit

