7.7. Subjects

7.7.1.Inclusion criteria for selection of subjects

- Patients for whom there is a care commitment for the alcohol program at the Addiction and Neuropsychiatry, Akademiska sjukhuset
- 18 years or older
- Meets at least 2 of the criteria for addiction / substance syndrome according to DSM-5
- Ability to understand and communicate in Swedish
- Ability to handle the technical equipment used in the study (breathalyzer + smartphone)
- Has a fixed point (accommodation, night rest place to charge the phone)

7.7.2.Exclusion criteria for selection of subjects

- Schizophrenia
- Substance syndrome related to substances other than alcohol and nicotine
- Impaired lung function (not able to achieve adequate exhalation volume for breathalyzer function)
- The patient is cared for within the framework of LVM
- Unsuitable to participate in the study according to the examiner's assessment
- Has not consumed any alcohol during the 4 weeks that baseline Time Line Follow Back refers to.
- Normalized CDT and PEth values in blood samples taken at visit 1.

7.7.3.Criteria and procedures for removing subjects from the study or suspending their participation

Substance syndrome related to substances other than alcohol and nicotine: Screening with urine sample and DUDIT is done at inclusion. The test result does not have to be available before the subject is included in the study, but should a positive screening test be reported, the subject should be removed from the study. No further samples are taken within the framework of the study.

Should the patient lose or otherwise lose the test product, it can be replaced (a limited number of times) and the patient does not need to be removed from the study if alcohol consumption is reported during the days when the measurements could not be performed and blood tests are performed to determine a new level of PEth / CDT . Phones that have fallen into the wrong hands or are misused in other ways can be deactivated by Kontigo Care. Contact Kontigo Care should this occur.

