9.1. Statistical design, method and analysis procedure

9.1.1. General

Continuous data will be summarized using descriptive statistics where the following parameters will be reported: number of observations, number of missing observations, mean, standard deviation, median, minimum and maximum. Categorical data will be presented with number (n) and percentage (%).

In addition to evaluation of all study data from the entire study period (12 months), 6-month data will also be evaluated.

Factors such as gender, severity of addiction, motivation, form of therapy and socio-economic factors will be considered as covariates in the statistical analyzes.

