- x) Compliance with TripleA. The proportion of measurements performed by those announced is calculated and reported for the TripleA arm.
- xi) Compliance with the agreed plan for visits to the care provider and / or visits to AA meetings. The treatment groups are compared with respect to the proportion of visits performed based on CRF data with a logistic regression model. For the TripleA arm, the corresponding data collected via TripleA and the correspondence between TripleA and CRF data are also evaluated.
- xii) Alcohol metabolites in the blood. Changes from baseline to 6 and 12 months, respectively, in PEth and CDT levels are calculated and the treatment groups are compared with an ANOVA model for repeated measurements.
- xiii) Evaluation of AUDIT data. The treatment arms will be compared with respect to:
 - xiv) - The proportion of patients who after 12 months have lowered their AUDIT score
 - xv) - The proportion of patients who after 12 months have lowered their AUDIT score to at least one zone
 - xvi) - Proportion of patients who after 12 months have a risk level <II (i.e. less than 6 AUDIT points for women, 8 AUDIT points for men).
- xvii) Evaluation of the number of "reds" and the number of missing blows in TripleA.

TripleA generates new types of high-resolution data that need to be handled in this and future clinical trials. In the simple case, the patient performs all agreed alcohol tests. For these, we can easily calculate the frequency of negative and positive alcohol tests in relation to a limit value for alcohol in the exhaled air. A fully sober patient has then probably performed 90 (3 / day) negative alcohol tests for 30 days in a month and can be considered 100% sober. A positive alcohol test ($> 0.1 \text{ mg / ml} = 0.2 \%$) gives a sobriety that is $1/90 = \sim 99\%$ or if it is calculated per day it will be 96.6% (29/30). What can be more complicated is to correlate this new type of high-resolution data with e.g. the number of days with large consumption from

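### The PEth comparison names neither a log scale nor a baseline PEth covariate; read as raw change from baseline, it can lose much of its precision to a few high starting values.

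*Combined protocol and SAP*

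**What the plan says.** Section 9.1.2.2, item xii, defines the outcome: "Changes from baseline to 6 and 12 months, respectively, in PEth and CDT levels are calculated". It then states that "the treatment groups are compared with an ANOVA model for repeated measurements". Section 7.2.2 gives PEth in µmol/L and CDT in per cent.

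Section 9 names no transformation, no rank method, no rule for results below a reporting limit and no baseline PEth term. On covariates, section 9.1.1 says: "Factors such as gender, severity of addiction, motivation, form of therapy and socio-economic factors will be considered as covariates in the statistical analyzes". Baseline PEth is not on that list.

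Four other statements bear on the choice of scale:

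- Section 4.6 on elimination: "The half-life is 4-7 days".
- Section 4.6 on interpretation: below 0.05 µmol/L means no or low sporadic intake, and the moderate band is 0.05 to 0.30. No upper limit is given.
- Section 7.7.2 lists as an exclusion: "Normalized CDT and PEth values in blood samples taken at visit 1".
- Section 7.3.7 on PEth sampling: "Time: Made at each visit". This applies to both arms.

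**The concern.** A marker eliminated by half-life falls in proportion to its level. On the raw scale a fall from 3.0 to 1.5 counts ten times as much as a fall from 0.30 to 0.15, although both are halvings. If baselines are spread over a wide range, the patients who start highest supply most of the variance of the change, and the arm comparison depends heavily on where those few patients were allocated. Leaving baseline PEth out of the model means that none of this variation is removed.

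Section 7.8.11 accepts that self-reported drinking may be distorted differently in the two arms, and section 7.1.3.2 brings in biomarkers to make self-report more reliable. PEth is scheduled alike in both arms, so it is a useful supporting check. An imprecise analysis would leave a null PEth result hard to interpret.

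**Working it through.** **1. The plan's own figure.** The only power calculation is for the primary endpoint (section 9.2): 30% against 60%, two-sided 5%, 80% power. With mean proportion 0.45,

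n = [1.960·√(2·0.45·0.55) + 0.8416·√(0.3·0.7 + 0.6·0.4)]² / 0.30² = (1.379 + 0.565)² / 0.09 ≈ 42 per arm.

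Allowing for 20% dropout, 42/0.8 = 52.5, so 53 per arm and 106 in total. This agrees with the plan. No such figure exists for PEth; 42 per arm is used below.

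**2. What raw change measures.** Four weeks is 28/7 = 4 to 28/4 = 7 half-lives. A patient who stops drinking keeps 1/2⁴ ≈ 6% to 1/2⁷ ≈ 1% of baseline. The raw change is then 94-99% of the baseline value with the sign reversed.

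**3. Assumed inputs (not in the documents).** Baseline PEth is log-normal with median 0.8 µmol/L, cut off below 0.05. Log-SD is 0.5 to 1.2 and the log-scale correlation of baseline with follow-up is 0.3 to 0.7. The control arm falls to 60% of baseline and the treatment effect is proportional. As a rough anchor for the spread: if 0.05 were the 2.5th percentile and 0.30 the median, the log-SD would be ln(6)/1.96 = 0.91.

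**4. Power at 42 per arm.** There were 4,000 simulated trials per setting, one time point and two-sided 5% tests. In each row the effect is set so that the log analysis with baseline has about 79% power. Ranges run over the three correlations 0.3, 0.5 and 0.7.

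| Log-SD | Raw change | Raw, baseline-adjusted | Log change | Log, baseline-adjusted | Share of raw-change sum of squares from the 4 highest baselines of 84 |
|---|---|---|---|---|---|
| 0.5 | 26-28% | 72-73% | 61-73% | 79% | 34-36% |
| 0.8 | 21-22% | 61-64% | 61-72% | 79% | 46-49% |
| 1.0 | 17-19% | 53-57% | 61-73% | 78-79% | 53-57% |
| 1.2 | 14-15% | 45-50% | 62-72% | 78-79% | 58-63% |

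At log-SD 1.0 and correlation 0.5 the four powers are 17%, 57%, 67% and 78%. Scale and baseline adjustment each contribute, and neither alone recovers the whole loss.

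**5. Other settings, raw change against baseline-adjusted log.**

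- Fixed halving of PEth relative to control: 74-91% against 100% at log-SD 0.5; 34-49% against 98-100% at 0.8; 20-30% against 90-99% at 1.0; 15-20% against 77-95% at 1.2.
- The same halving, control arm not falling, correlation 0.5: 72%, 47% and 31% against 99%, 95% and 85% at log-SD 0.8, 1.0 and 1.2.
- 15% against 35% abstinent, with a ratio of 0.7 in the rest, log-SD 0.8 to 1.2: 10-29% against 68-82%.
- Average of 6 and 12 months, ratio 0.55, log-SD 0.8 to 1.2: 14-43% against 72-100%.
- No treatment effect: raw change rejects in 4.4% of trials, so type I error holds.

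**6. Mildest case.** With no skew and equal variances at baseline and follow-up, the variance of the unadjusted change relative to the adjusted analysis is 2(1−ρ)/(1−ρ²) = 2/(1+ρ). Where the adjusted analysis has 80% power, the unadjusted power is Φ(2.80/√(2/(1+ρ)) − 1.96). This gives 62% at ρ = 0.3 and 73% at ρ = 0.7.

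**The case against.** - **The plan does not say raw.** This is correct. It speaks of changes in levels and is silent on scale. Untransformed change is the natural reading, but what the text establishes is that scale and baseline adjustment are not specified.
- **The size is assumed.** This also stands. No PEth median, spread or effect is given. A log-normal baseline with a proportional effect favours the log test by construction. A half-life describes washout after stopping; it does not prove that effects in continuing drinkers are proportional.
- **The simulated test is simpler than the plan's model.** The main runs use one time point and no covariates. The two-time-point runs point the same way, but covariates such as severity of addiction, if used, might recover some precision.
- **The entry cut-off is not strict.** The exclusion names both markers. If both must be normal, a patient with normal PEth and raised CDT could enter. This affects the low end, not the high values that drive the variance.

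A reader might infer that PEth is the main objective check on the primary result. The documents do not support that. Section 4.6 says that PEth misses occasional intoxication, whereas one heavy drinking day decides the primary endpoint. Other cross-checks exist: blood results feed the self-report interview and discrepancies can be recorded in the CRF (section 7.3.2), and section 9.1.3 compares self-report analyses with ones that add blood and TripleA data.

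A reader might also infer that a null PEth result is likely whatever TripleA does. With a true halving and log-SD 0.5, raw change still has 74-91% power. Nor is there support for extending the log scale to CDT: it is reported as a percentage, no skew is shown, and it was not simulated.

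**Conclusion.** The point holds as a gap in prespecification with a probable loss of precision. Item xii fixes neither the scale nor a baseline PEth term, and the document's own account of PEth (half-life elimination, entry restricted at the low end only) favours a log scale with baseline adjustment. The loss is large in the skewed settings where the adjusted log analysis has about 79% power: raw change then has 14-28%. It is modest, 80% to 62-73%, without skew and with equal variances. Which applies depends on a PEth distribution that the documents do not give.

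The missing baseline term matters as well as the scale, so blaming the scale alone would be wrong. The consequence is limited to one secondary endpoint that was never powered. Type I error stays near 5% and no bias arises. It is worth changing because it is cheap, not because it threatens the trial's conclusion.

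**What to change.** In item xii, specify that log(PEth) is analysed in the repeated-measures model with log baseline PEth as covariate. Set results below the laboratory's reporting limit to half that limit, and state the limit. Report the TripleA/control ratio of geometric means with 95% CI at 6 and 12 months, keeping raw medians as description. For CDT, add baseline CDT as covariate and leave the scale as it is.

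The cost is one or two SAP sentences, with no new samples or visits. There are two small drawbacks: the effect becomes a ratio, and a fixed value stands in for results below the limit.

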7.5.2. Loss of individual values

Missed blows are discussed with the patient during the visits. If the patient has a plausible explanation for the lack of a single puff, the caregiver can state this in the system, and indicate whether or not there should have been alcohol in the exhaled air at the time in question. A patient who so wishes may submit an extra blood sample to prove that he has been sober during the period when measurement values are missing.

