patient-reported data in TLFB form. If there are 3 positive blows in one day, it is very likely also a heavy drinking day (≥ 4 standard glasses / day for women, ≥ 5 standard glasses / day for men), which is medically serious. If there are alcohol tests performed in the evening 3 different days with just over 0.2 %, it can correspond to 2 glasses of wine for dinner - which can be completely acceptable if the goal is to reduce drinking and its somatic and psychological consequences (risk reduction). If you detect around 0.2 % in the morning 3 different days, it can be serious and very well mean 3 heavy drinking days where the alcohol consumption took place after the last alcohol test in the evening and the body did not have time to burn all alcohol before the next test in the morning.

The second thing to deal with is missed alcohol tests. These may be due to the patient being sober but for various reasons not being able to perform the alcohol test in time (not noticed the notification, flight, mobile data shadow, etc.) or relapse into alcohol consumption. Here, the patient can contact the care provider (or vice versa) and clarify what happened.

The caregiver has the opportunity to enter a new classification for an individual test in the caregiver portal, which means that the database will contain supplementary information - without overwriting the basic status. The following options are available for missed tests:

- No alcohol
- Alcohol could not be excluded
- Technical issue.

If the default status is "Alcohol could not be excluded", the following status comments can be selected:

- No alcohol
- Technical issue.

If the basic status is "Technical error", the following status comments can be selected:

- No alcohol
- Alcohol could not be excluded

The patient also has an opportunity to show that they have not had a relapse by submitting blood samples for analysis of PEth and CDT. The caregiver can then reclassify the missed alcohol tests as above.

Even if the caregiver indicates a new classification on a test performed or missed, the original data always remains, which is so that the percentage sobriety can be calculated in two ways:

- o Proportion of sober tests based on all alcohol tests performed.
- o Corrected proportion of sober tests where both performed and missed alcohol tests are taken into account, with the classification made by the care provider as above.

9.1.3.Explorative analyses

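### PEth and CDT samples may clear an individual missed breath test as *No alcohol*, although section 4.6 says these markers can miss a single episode, so a short relapse can be hidden from both planned sobriety percentages

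*Combined protocol and SAP*

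**What the plan says.** Three places in the protocol give an extra blood sample the role of evidence about a missed breath test.

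- Section 9.1.2.2, item xvii: "The patient also has an opportunity to show that they have not had a relapse by submitting blood samples for analysis of PEth and CDT". It continues: "The caregiver can then reclassify the missed alcohol tests as above". The options for a missed test are *No alcohol*, a status saying that alcohol cannot be ruled out (below, *not excluded*), and a technical problem.
- Section 7.5.2: a patient "may submit an extra blood sample to prove that he has been sober during the period when measurement values are missing".
- Section 5.2 offers the same sample as a way to prove sobriety, as relief for the stress of a missed test.

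No section gives a marker cut-off, a sampling deadline or a rule that links a result to a status.

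Section 4.6 describes what the two markers can show:

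- On PEth: "PEth is specific for alcohol, but does not detect occasional intoxication".
- PEth values below 0.05 µmol/L "indicate no or low sporadic alcohol consumption".
- For the range 0.05-0.30 µmol/L it adds that "even occasional very large intakes of alcohol can probably give measured values in this range".
- On CDT: "Single major alcohol intakes do not affect CDT levels".

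Section 9.1.2.2 keeps the original test status and plans two sobriety percentages. One is based on performed tests only. The other is a corrected proportion that counts performed and missed tests with the caregiver's classification.

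**The concern.** A missed test concerns one 60-minute slot on one day (section 7.6.1). PEth and CDT reflect intake over weeks. By the protocol's own description, a patient can drink on one occasion, miss the tests around it, and later give a sample with unchanged CDT and low PEth. The rule then permits *No alcohol* for those tests. The written rule can therefore give a wrong answer when followed as intended; more than a missing detail is involved.

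The status is used in several places:

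- **Corrected sobriety proportion** (9.1.2.2, item xvii): uses the caregiver's classification directly. It is reported for the TripleA arm only.
- **Exploratory analyses** (9.1.3): use corrected values for sober days, and correlate TripleA results with PEth and CDT. If blood-corrected values enter that correlation it is partly circular, because the same markers have helped to set the TripleA status.
- **Time to relapse** (9.1.2.2): lists TripleA among its sources, without saying whether the original or the reclassified status counts. This endpoint is compared between arms, while reclassification exists in one arm only.

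**Working it through.** **1. The plan's own example.** Section 9.1.2.2 takes 3 tests a day for 30 days, 90 tests in all, with one positive.

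- Per test: 89/90 = 98.9% (plan: about 99%).
- Per day: 29/30 = 96.67% (plan: 96.6%).

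Both figures reproduce.

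**2. The same month with missed tests.** Define

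- A = sober performed tests / performed tests;
- B = (sober performed tests + missed tests classed *No alcohol*) / (performed + missed tests).

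Suppose the patient drinks on one day, misses the tests on that day, and all other tests are negative.

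| Missed tests | A | B, cleared as *No alcohol* | B, *not excluded* |
|---|---|---|---|
| 3 | 87/87 = 100% | 90/90 = 100% | 87/90 = 96.7% |
| 1 | 89/89 = 100% | 90/90 = 100% | 89/90 = 98.9% |

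Once the tests are cleared, neither percentage shows the event. A drops the missed tests from its denominator, and B counts them as sober. The last column assumes that a *not excluded* test counts as not sober. The plan does not say how a missed test without any comment is counted in B.

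**3. Would the sample reveal the episode?** For CDT, section 4.6 says no. For PEth it makes two statements that need reconciling: occasional intoxication is not detected, yet a very large occasional intake can probably give 0.05-0.30 µmol/L. Take the more favourable statement and suppose that the episode lifted PEth to between 0.10 and 0.30. Section 4.6 also states: "The half-life is 4-7 days". Then

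days to reach 0.05 = half-life × log2(start / 0.05).

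- From 0.10: log2(2) = 1 half-life, so 4 to 7 days.
- From 0.30: log2(6) = 2.58 half-lives, so 10.3 to 18.1 days.

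With no sampling deadline, even an episode that did raise PEth can look clean after about 4 to 18 days. The 0.05 threshold and the 0.10 start are assumptions made for this check; the plan sets no clearing threshold.

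**4. What still shows the event.** The original status is stored, item x reports performed against announced tests, and item xvii counts missed tests. These show that tests were missed. They do not separate a drinking day from a flight or a lost connection.

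**The case against.** The strongest reply is that the plan is more guarded than the rule suggests. Section 4.6 itself lists confirming sobriety over recent weeks as a use of PEth. Reclassification is optional, *not excluded* is also available, and the original data stay in the database. All of that stands, and it limits the point. But sobriety over recent weeks is a different question from no alcohol around one test, and the optional status comes with no criterion for choosing it.

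Four stronger readings are tempting and are not supported:

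- **Relapses are erased.** They are not. The basic status is kept, and missed tests still appear in items x and xvii. What is lost is their visibility in the two percentages.
- **Newly sober patients cannot be cleared.** With a half-life of 4-7 days, PEth takes 10-18 days to fall from 0.30 to 0.05, and 17-30 days from an assumed 1.0, so a blood result may be unhelpful for a time. But the plan requires no normal value, gives no starting values, and accepts a plausible explanation without blood (7.5.2).
- **The markers never register a single episode.** This fits the text on CDT. For PEth the text is mixed.
- **The primary endpoint is biased.** It comes from the patient's own TLFB report, which the caregiver may not change without consent (7.3.2). A missed test is meant to prompt an entry above 0 glasses, not a heavy drinking day, and no section says that a *No alcohol* status cancels this. The caregiver can also record in the CRF signs of intake that disagree with the TLFB. A cleared test might weaken the TLFB discussion, but that route is indirect.

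For time to relapse, it is also fair to say that the plan never states that a missed test counts as a relapse, and section 7.2.2 rests on the patient's own information. The effect there is possible, not shown.

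**Conclusion.** The point holds in limited form. The rule that lets PEth and CDT support *No alcohol* for an individual missed test conflicts with section 4.6. In the illustrated month it moves the corrected proportion from 96.7% to 100%, a difference of 3/90 = 3.3 percentage points, and leaves no sign of the drinking day in either percentage. With one missed test the difference is 1/90 = 1.1 points.

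These sizes are illustrations. They assume that the caregiver uses the blood route, that every other test is negative, and that a *not excluded* test counts as not sober. The documents do not say how often tests will be missed or cleared in this way.

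The consequence is confined to the TripleA-arm corrected proportion, the exploratory work in 9.1.3 and possibly time to relapse. The definition of the primary endpoint and the sample size are not touched. The contradiction should be corrected because the repair is cheap and the corrected figure cannot otherwise be interpreted.

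**What to change.** Choose one of two consistent options in sections 9.1.2.2 and 7.5.2.

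1. **Preferred.** PEth and CDT alone do not change an individual missed test to *No alcohol*. The patient may still give the sample, and it is recorded as supportive information on recent weeks. The existing route of a plausible explanation stays.
2. **If blood-based reclassification is kept.** Flag each test cleared in this way, and report the corrected proportion a second time with those tests counted as *not excluded*.

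Under either option:

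- Use the original status, not the blood-corrected one, when correlating TripleA results with PEth and CDT in 9.1.3.
- State which status feeds time to relapse, and how a missed test without a comment is counted in the corrected proportion.
- Replace *prove* in sections 5.2 and 7.5.2 with wording that matches section 4.6, and reconcile the two statements on PEth in section 4.6.

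The cost is protocol wording and, under the second option, one extra tabulation. The corrected sobriety figure in the TripleA arm may look slightly less favourable.
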